2.2.4 Pharmacokinetic Analysis Set

The Pharmacokinetic Analysis Set (PAS) includes all patients who provide at least one evaluable pharmacokinetics (PK) concentration. For a concentration to be evaluable, patients are required to:

- For samples on Week 2
 - take the same dose of eltrombopag for all dosing days prior to sampling on Week 2
 - for pre-dose sample, do not vomit within 4 hours after the dosing of eltrombopag prior to sampling
 - for post-dose samples, do not vomit within 4 hours after the dosing of eltrombopag on the sampling day
- For all pre-dose samples, have the sample collected before the next dose administration

2.2.5 Screening failures

Patients who sign an informed consent form but fail to start on study treatment for any reason will be considered a screen failure.

2.2.6 Subgroups of interest

The following subgroups of interest may be used in analyses:

- Age (<60, ≥ 60 years)
- Ethnicity (East/South East (E/SE) Asian vs Other)
- Responder status (Responder, Non-responder) – see [Section 2.5.1](#) for definition

2.3 Patient disposition, demographics and other baseline characteristics

The Full Analysis Set (FAS) will be used for all baseline and demographic summaries and listings unless otherwise specified.

2.3.1 Patient disposition

Disposition data will be summarised descriptively and listed. Summaries will include number and percentage (%) of patients who; complete a study phase (screening, treatment period 1, treatment period 2, post treatment follow-up and/or treatment discontinuation follow-up), patients who continue to the next phase, patients who discontinue a study phase with primary reason as reported on the disposition eCRF pages. Number (%) of patients who permanently discontinued study treatment with reason, as reported in the dose administration record eCRF pages will also be provided.

Informed consent and inclusion/exclusion criteria data will also be listed.

Data will be listed for screening failures.

The denominator will be based on the number of patients who enter the respective study phase (4 phases are used under PA1 and 2 phases are used under PA2, see study design figures in [Section 1.1](#)).

2.3.2 Patient demographics and other baseline characteristics

Demographic and other baseline data (e.g. medical history, transfusion history, diagnosis and extent of cancer, and eastern cooperative oncology group (ECOG) performance status etc.) will be summarised descriptively and listed. Age by category will also be summarised.

Demographic data for screen failure patients will be listed.

Demographic data will also be summarised by age sub-groups, ethnicity and/or responder status.

Medical history

Medical histories and current medical conditions at baseline will be summarised separately for ongoing and historical medical conditions by primary system organ class (SOC) and preferred term (PT). Medical history and current medical conditions will be coded using the latest version of the Medical Dictionary for Regulatory Activities (MedDRA) at the time of analysis. Listings will be provided of all data.

Transfusion history

Transfusion history for platelets and for red blood cells (RBCs) in the 4-weeks prior to initiation of dosing of eltrombopag and cyclosporine will be summarised and listed. The number of platelet/RBCs transfusions and time since last platelet/RBCs transfusion will be provided.

Time since last platelet/RBCs transfusion (in days) = Start date of treatment – start date of last platelet/RBCs transfusion.

Analyses sets

The number (%) of patients in each analysis set (defined in [Section 2.2](#)) will be summarised.

2.4 Treatments (study treatment, concomitant therapies and compliance)

Eltrombopag (film-coated tablets) will be administered orally, once daily for 6 months.

Cyclosporine (soft-gelatin capsules) will be administered orally, twice daily for the first 6 months and for a further 18 months (tapering regime for responder patients only).

All patients must have safety evaluations for 30 days, after the last dose of study treatment.

2.4.1 Study treatment

Duration of study drug exposure (months), actual cumulative dose, actual dose intensity (DI) and relative dose intensity (RDI) will be summarised separately for each study drug (eltrombopag and cyclosporine) for the safety set.

The number of patients with dose changes, interruptions and permanent discontinuations will be presented, along with reasons for the dose change/interruption/permanent discontinuation for each study drug.

Duration of exposure (months) will also be categorized and summarised using the following time intervals:

- Eltrombopag: <1, ≥ 1, ≥ 2, ≥ 3, ≥ 4, ≥ 5, ≥ 6
- Cyclosporine: <1, ≥ 1, ≥ 2, ≥ 3, ≥ 4, ≥ 5, ≥ 6, ≥ 12, ≥ 18, ≥ 24

Listings will be provided of all data.

2.4.2 Prior, concomitant and post therapies

Medications and significant non-drug therapies prior to and after the start of the study treatment will be coded according to the world health organization (WHO) Drug Reference List and summarised by anatomical therapeutic chemical (ATC) classification and preferred term.

Summary tables for concomitant medications and concomitant non-drug therapies for the safety set will be provided. Prior, concomitant and post study treatment medications and non-drug therapies will be listed for the safety set. Medications and therapies outside of the on-treatment period will be flagged.

Listings will be provided.

2.4.3 Protocol deviations

The number (%) of patients with protocol deviations will be summarised by deviation category (as specified in the latest version of the study data handling plan (DHP) at the time of analysis) and overall for the FAS. All protocol deviations will be listed, flagging those leading to the exclusion of a patient from an analysis set. Protocol deviations will be listed for screening failures (if any).

2.4.4 Handling of missing values

For analyses prior to the final analysis (at 24 months), if the date of last administration of study drug is completely missing and there is no end of treatment eCRF page, the patient is considered as on-going and the earliest of; death date, last contact date or cut-off date, will be used as the 'last dosing date' for calculation/derivation purposes e.g. durations. Last administration date should not be missing for the final analyses.

2.5 Analysis of the primary objective

The primary objective of this study is to evaluate the efficacy of eltrombopag+cyclosporine as first-line therapy as measured by the overall hematologic response rate by 6 months. That is, after all enrolled patients have completed 6 months of study treatment or discontinued study treatment or study prior to 6 months. Efficacy analyses and listings are based on the FAS.

2.5.1 Primary endpoint

The overall hematologic response rate (ORR) is defined as the proportion of patients achieving complete response (CR) and partial response (PR) defined as follows:

Partial response (PR) is defined as any two of the following parameters at two consecutive, scheduled visit measurements at least 7 days apart during the first 6 months of study (and not sufficient for CR) and no platelet transfusions within 7 days of platelet measurement (can still be a PR if ANC and reticulocyte measurements are valid):

- Absolute neutrophil count (ANC) $\geq 500/\mu\text{L}$
- Platelet count $\geq 20\,000/\mu\text{L}$
- Reticulocyte count $\geq 60\,000/\mu\text{L}$ (automated)

Complete response (CR) is defined as all three parameters meet the following criteria at two consecutive, scheduled visit measurements at least 7 days apart during the first 6 months of study and no platelet transfusions within 7 days of platelet measurement and no RBC transfusion with 14 days of the hemoglobin measurements:

- ANC $\geq 1\,000/\mu\text{L}$
- Platelet count $\geq 100\,000/\mu\text{L}$
- Hemoglobin $\geq 10\text{ g/dL}$

ORR_6 = Number of patients who achieved hematologic response by 6 months/Number of patients in the FAS.

Responder status: If any patient achieves hematologic response (either CR or PR) any time on or before the 6 months visit, they will be considered a **responder**, else they are a **non-responder**.

The point estimate along with the corresponding exact 95% confidence interval using Clopper and Pearson exact method will be presented for ORR_6.

Day 10 (plat 8 000) sample at 10:00 and platelet transfusion Day 10 11:00 (plat 60 000)—assume transfusion is always after the blood sample Day 10 sample is valid for efficacy.

Day 11 to Day 16 not valid (Day 11 (50 000), 12 (45 000), 13, 14, 15, 16 (transfusion minimal impact by day 7) not valid). Both Day 10 and Day 17 samples are valid for efficacy

Handling of missing values/discontinuations

If any patient achieves overall hematologic response any time before 6 months but discontinues prior to 6 months or has missing parameters required for assessing overall hematologic response at any point after achieving the first response, they will be considered as responders.

Due to COVID19 situation some patients may have local instead of central lab results for scheduled visits. For all patients, local results (including the visit window period) will be used if all 4 results of the efficacy parameters (hemoglobin, neutrophils, reticulocytes, platelets) from the central laboratory are not available for a scheduled visit.

2.5.2 Supportive analyses

The ORR **by** 6 months (primary analysis) will be repeated on the PPS.

The ORR **by** 6 months (primary analysis) will also be summarised by age sub-groups and/or ethnicity using the FAS and/or PPS.

The ORR **at** 6 months will be summarised using the FAS as follows:

- The overall hematologic response will be calculated at 6 months (based on assessment at 6 months visit and the previous visit at least 7 days apart) based on the evaluable patients (i.e., patients for whom data is available at 6 months). Thus if a patient has missing laboratory parameters at 6 months or the prior visit at least 7 days apart required to calculate CR or PR, or if the patient discontinued earlier than 6 months, then the patient will be considered as a non-responder.
- ORR_a6 = Number of patients who achieved hematologic response at 6 months/Number of patients in the FAS.

2.6 Analysis of secondary efficacy objective(s)

All secondary efficacy analyses will be performed on the FAS, unless otherwise specified.

Secondary objectives will be summarised in the 6 and 24 months CSRs with data reported cumulatively. Listings will be provided.

2.6.1 ORR by 3 months, at 12 months and at 24 months

The ORR by 3 months will be evaluated and summarised as for the ORR by 6 months, i.e. if any patient achieves hematologic response any time on or before the month 3 visit, they will be considered a **3 month responder**, else they are a **3 month non-responder**.

- ORR_3 = Number of patients who achieved hematologic response by 3 months/Number of patients in the FAS.
- The ORR **by** 3 months will be repeated on the PPS.
- The ORR **by** 3 months will also be summarised by age sub-groups and/or ethnicity using the FAS and/or PPS.

The ORR at 12 months and at 24 months will be summarised as for the ORR at 6 months. If any 6 month responder achieves hematologic response at 12 months (24 months) visit, they will be considered at **12 months (24 months) responder**, else they are at **12 month (24 month) non-**

responder. The 12 months (24 months) visit will be the confirmatory visit of the most recent visit assessment prior to this assessment (at least 7 days apart).

- ORR_a12 (ORR_a24) = Number of patients who achieved hematologic response at 12 months (24 months)/Number of patients in the FAS.
- The ORR **at** 12 months (24 months) will be repeated on the PPS.
- The ORR **at** 12 months (24 months) will also be summarised by age sub-groups and/or ethnicity using the FAS and/or PPS.

2.6.2 Duration of hematologic response

The time from start of the first hematologic response (the initial assessment, not the confirmatory assessment, of either CR or PR whichever occurs first by 6 months) to the date of first relapse will be derived as:

- Duration of first hematologic response (days) = End date (Date of first relapse) – start date of first hematologic response + 1

Longest duration will also be presented:

- Longest duration of hematologic response (days) = End date (Date of relapse) – start date of longest hematologic response + 1

Relapse is defined as no longer meeting the definition of PR (and not CR).

The duration of hematological response will be estimated using Kaplan-Meier method and the median time to relapse will be presented along with 95% confidence interval. If no relapse occurs, the patient will be **censored** at the date of last contact.

2.6.3 Relapse rate

The number (%) of responders who relapse during the study will be reported by 6 and 24 months on a cumulative basis and will be summarised together with the corresponding exact 95% confidence interval using Clopper and Pearson exact method.

2.6.4 Clonal evolution

The number (%) of patients along with corresponding exact 95% confidence interval (using Clopper and Pearson exact method) with possible clonal evolution to myelodysplasia, paroxysmal nocturnal hemoglobinuria (PNH) and/or acute leukemia occurring during the study will be summarised by 6 and 24 months. Clonal evolution to each group is defined as:

- **myelodysplasia:** a new marrow cytogenic abnormality with complex karyotype marked as 'Yes'
 - taken from the 'Cytogenetics / Other Abnormalities' eCRF page.
- **PNH:** a clone of peripheral blood GPI-deficient (%) having cumulative PNH sub-type of type 2 RBC% and type 3 RBC% value of <10% at baseline that rose to >50% on study
 - taken from the 'Flow cytometry' eCRF page using the parameter 'Peripheral blood GPI-deficient (%)'
 - Any rise (local or central) will be considered
- **acute leukemia:** >20% peripheral blood and/or marrow blasts post baseline

- marrow blasts are taken from the 'Bone Marrow Aspirate' or the 'Bone Marrow Biopsy' eCRF page using the 'Blast Cells (%)' parameter

Programmed listing results will be reviewed by clinical and/or steering committee members and confirmed cases of clonal evolution will be discussed in the CSR.

2.6.5 Blood (RBC) and platelet transfusions

The number (%) of patients with corresponding 95% confidence interval (using Clopper and Pearson exact method) will be summarised by 6 and 24 months (responders only) for patients:

- who received at least one platelet transfusion
- who received at least one RBC transfusion
- with platelet transfusion independence
- with RBC transfusion independence

Transfusion independency is considered if transfusions are not required in at least a 28 day period for platelet transfusions and at least 56 day period for RBC transfusions.

In addition the duration of the longest interval without a platelet or RBC transfusion by 6 months and by 24 months (responders only) will be summarised using Kaplan-Meier analysis and the median longest duration will be presented along with 95% confidence interval.

- Longest duration of platelet transfusion independence (days) = End date of longest interval – start date of longest interval + 1
- Longest duration of RBC transfusion independence (days) = End date of longest interval – start date of longest interval + 1

Note that:

- the start date of the longest interval might use the patient's first dose date or the patient's last transfusion date + 1
- the end date of the longest interval might use the patient's first transfusion date – 1 or if no end date of longest interval without a platelet or RBC transfusion occurs, the patient will be **censored** at the date of last contact.

Listings will be provided.

Transfusions packed red blood cells, platelets and longest duration of transfusion independence will be also summarised by age sub-groups and/or ethnicity.

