4. To evaluate the clonal evolution to myelodysplasia, paroxysmal nocturnal hemoglobinuria (PNH), and leukemia	Percentage of patients with evolution to myelodysplasia, PNH, and acute leukemia occurring at any time during the study	
5. To evaluate red blood cells (RBC) transfusion independence	Percentage of patients who are RBC transfusion independent at least once by 6 months and by 24 months. Independence defined as no RBC transfusion for at least 56 days	
6. To evaluate platelet transfusion independence	Percentage of patients who are platelet transfusion independent at least once by 6 months and by 24 months. Independence defined as no platelet transfusion for at least 28 days.	
7. To evaluate the longest interval without a platelet or RBC transfusion	Duration of longest interval without a platelet transfusion by 6 months and by 24 months Duration of longest interval without a RBC transfusion by 6 months and by 24 months	
8. To evaluate the effect of Eltrombopag and cyclosporine on patient symptoms and health related quality of life	Change in scores from baseline to 6 months and 24 months on the FACT-G, FACT-TH18, and FACT-Fatigue scales	

Objective	Endpoint	Analysis
9. To evaluate the safety and tolerability of eltrombopag + cyclosporine	Safety will be assessed by: 
• Frequency and severity of AEs, serious AEs (SAEs) based on the Common Terminology Criteria of Adverse Events (CTCAE version 4. 03), and AEs leading to discontinuation, and evaluating changes in laboratory values within 6 months and within 24 months (responders only)• Incidence of the following adverse events of special interest	Refer to Section 10.5.3
10. To characterize the PK of eltrombopag when combined to cyclosporine	Plasma PK parameters of eltrombopag 2 weeks and trough concentrations at 1 month 1, 2 months, 3 months, and 6 months	Refer to Section 10.5.4

Objective	Endpoint	Analysis
*Overall hematologic response = patients with complete response (CR) + patients with partial response (PR)		
a. Partial response is defined as any two of the following parameters at two consecutive, scheduled visit measurements at least 7 days apart during the study and no platelet transfusions within 7 days of platelet measurement (can still be a responder if ANC and reticulocyte measurements are valid):		

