- with RBC transfusion independence

Transfusion independency is considered if transfusions are not required in at least a 28 day period for platelet transfusions and at least 56 day period for RBC transfusions.

In addition the duration of the longest interval without a platelet or RBC transfusion by 6 months and by 24 months (responders only) will be summarised using Kaplan-Meier analysis.

The platelet and RBC transfusions will be evaluated separately.

Quality of life

FACT-G, FACIT-Fatigue and FACT-TH18 responses will be generated in accordance with the respective scoring manual. Descriptive statistics will be used to summarize the raw and absolute change from baseline to each assessment visit. Patients with an evaluable baseline score and at least one evaluable post baseline score during the treatment period will be included in the

change from baseline analyses. Missing items data in a scale will be handled based on each instrument manual. All PRO analyses will include data as imputed according to the scoring manual. No imputation will be applied if the total or subscale scores are missing at a visit. Summaries will be reported by 6 months and 24 months (responders only).

Additional analyses may be performed if deemed necessary. Such analyses will be defined in the SAP.

All of the above analyses will be done on the FAS.

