2.2.1 Full Analysis Set

The Full Analysis Set (FAS) includes all patients who received at least one dose of study treatment (eltrombopag or cyclosporine).

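### Transfusion independence has no baseline condition, so its percentage can mix patients who became independent with patients who had no transfusion before treatment

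*SAP*

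**What the plan says.** For platelets, the criterion in SAP 2.6.5 is "Transfusion independency is considered if transfusions are not required in at least a 28 day period for platelet transfusions". The red-cell criterion, given in the same place, is "at least 56 day period for RBC transfusions". Protocol Section 3, Table 3-1 (objectives 5 and 6) makes a single qualifying stretch sufficient. For platelets the endpoint is "Percentage of patients who are platelet transfusion independent at least once by 6 months and by 24 months", and the red-cell endpoint is built the same way.

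On the population, SAP 2.6 states "All secondary efficacy analyses will be performed on the FAS, unless otherwise specified". Protocol 10.5.1 closes its secondary analyses, these included, with "All of the above analyses will be done on the FAS". SAP 2.2.1 defines that set without reference to transfusion: "The Full Analysis Set (FAS) includes all patients who received at least one dose of study treatment (eltrombopag or cyclosporine"). The SAP 2.6.5 results "will be summarised by 6 and 24 months (responders only) for patients" with several transfusion outcomes. The Protocol summary makes the split explicit: all patients at 6 months, responders at 24 months.

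For the longest transfusion-free interval, SAP 2.6.5 allows the start date to be the first dose date. SAP 2.3.2 summarises and lists "Transfusion history for platelets and for red blood cells (RBCs) in the 4-weeks prior to initiation of dosing", with the number of transfusions and the time since the last one. That history does not enter the independence definition or its denominator. The subgroups for transfusion outputs are age and ethnicity (SAP 2.2.6 and 2.6.5).

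**The concern.** The trial has no comparator, so each patient's state before treatment is the only internal reference for a transfusion outcome. A percentage of transfusion-independent patients is easily read as the share released from transfusion by the regimen. As defined, it is the share with at least one long enough transfusion-free stretch on study, whatever their history.

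Patients without a recent transfusion can enter. Protocol 5.2 requires two of three cytopenias. Low neutrophils plus low reticulocytes suffice, so not every patient must have a low platelet count, and hemoglobin is not a criterion. Protocol 6.4.1.1 recommends platelets below 10 000/µL, below 20 000/µL with active bleeding, or as medically necessary. It recommends red cells below 8 g/dL or for symptoms. A patient can meet the entry criteria without reaching either numeric trigger.

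The neighbouring endpoint shows that the SAP does anchor to baseline elsewhere: in SAP 2.6.4, evolution to PNH requires a clone below 10% at baseline that rises above 50%. At stake is how a key secondary result can be interpreted.

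**Working it through.** **The plan's own figure.** There is none to reproduce. Neither document states an expected rate, a power or a threshold for transfusion independence, and Protocol 10.9 marks secondary power as not applicable.

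**Inputs from the documents.** N = 54 enrolled (SAP Section 1); 28-day and 56-day criteria met at least once; FAS at 6 months, responders at 24 months; no baseline condition.

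**Inputs assumed, because the documents do not give them.**
- f, the share with no transfusion of that type before treatment: 0, or 3 to 16 of 54 (about 6% to 30%)
- pD, the rate of independence among patients transfused before treatment: 30% to 60%
- pI, the rate among patients not transfused before treatment: 100% or about 80%

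**Formula.** The overall rate is f × pI + (1 − f) × pD. Subtracting pD gives the excess over the rate in previously transfused patients: f × (pI − pD). It is zero if f = 0 or pI = pD.

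**Worked example.** Take 11 of 54 not transfused before treatment, all 11 later independent, and 17 of the other 43 independent.
- Overall: (11 + 17)/54 = 28/54 = 51.9%
- Previously transfused: 17/43 = 39.5%
- Excess: 11/54 × (1 − 17/43) = 0.2037 × 0.6047 = 0.123, or 12.3 points

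**Sensitivity, with pD near 40%** (whole patients, Clopper-Pearson 95% intervals):

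| Not transfused before | Overall, pI = 100% | Previously transfused | Excess, pI = 100% | Overall, pI about 80% | Excess, pI about 80% |
|---|---|---|---|---|---|
| 0 of 54 | 22/54 = 40.7% (27.6–55.0) | 22/54 = 40.7% (27.6–55.0) | 0 | 22/54 = 40.7% | 0 |
| 5 of 54 | 25/54 = 46.3% (32.6–60.4) | 20/49 = 40.8% (27.0–55.8) | +5.5 | 24/54 = 44.4% | +3.6 |
| 11 of 54 | 28/54 = 51.9% (37.8–65.7) | 17/43 = 39.5% (25.0–55.6) | +12.3 | 26/54 = 48.1% | +8.6 |
| 16 of 54 | 31/54 = 57.4% (43.2–70.8) | 15/38 = 39.5% (24.0–56.6) | +17.9 | 28/54 = 51.9% | +12.4 |

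With 3 to 16 patients not transfused and pD from 30% to 60%, the excess runs from 2.2 to 21.1 points at pI = 100%, and from 0.3 to 15.5 points at pI of about 80%.

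**At 24 months** the same algebra holds with responders as the base. The table does not describe that group, because the documents do not give its size or transfusion history.

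**The case against.** A reader might infer four stronger things, and the documents support none of them.

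- **That the reported percentage is inflated.** The share of patients without prior transfusion is not stated. All patients have severe disease with at least two marked cytopenias, so it could be small or zero.
- **That patients not transfused beforehand succeed almost automatically.** These patients are treatment-naïve and may have presented recently, so a clear 4 weeks need not mean lasting lack of need. Counts can fall after Day 1, and red-cell independence takes 56 clear days. Early death or discontinuation can prevent success: the Amendment 2 rationale reports four on-treatment deaths and one post-treatment death when 31 patients had been enrolled. This is why pI is varied above.
- **That all patients are counted throughout.** That is true at 6 months only.
- **That the FAS row should give way to a previously-transfused row.** SAP Section 1 records the lock for the primary analysis on 09-Dec-2020 and a primary CSR already written. A change of main row now would redefine a protocol endpoint post hoc.

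The plan also has a partial answer. SAP 2.6.5 reports the numbers with at least one platelet and at least one red-cell transfusion, SAP 2.3.2 tabulates the pre-treatment history, and listings are provided. The protocol endpoint describes a status and does not claim conversion.

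All of this limits the size and tone of the point. What stands is that separate marginal tables cannot show how many of the independent patients had no recent transfusion, and no planned table named in the SAP crosses the two. The table shells are a separate document and were not available.

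**Conclusion.** The definition has no baseline transfusion condition, and the percentage can mix two kinds of patient in the FAS by 6 months and in responders by 24 months. This can overstate the apparent benefit by f × (pI − pD), an amount that cannot be derived from the documents. The 12.3-point example rests on assumed values: 11 of 54 not transfused beforehand, all of them independent later, and 17 of 43 of the others independent. With no such patients the excess is nil.

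The endpoint is descriptive and lies outside both success criteria in Protocol 10.4.2, so the primary conclusion does not change. This is a cheap improvement to a secondary table.

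**What to change.** Keep the pre-specified row (FAS by 6 months, responders by 24 months) as the main result. For the final CSR, add two rows under each of platelet and red-cell independence:

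1. patients with at least one transfusion of that type in the 4 weeks before first dose;
2. patients with none.

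Give n/N, the percentage and the Clopper-Pearson interval for each. Label the rows as added after the 6-month analysis and record them in SAP Section 4, which already lists added subgroup analyses of transfusion information. Add a footnote that for red cells the 4-week history is half of the 56-day criterion (28/56), so baseline status is approximate and some patients with red-cell need may be classed as having none.

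No new data are needed. The cost is the extra rows and less precision. In the worked example the interval widens from 27.9 points (37.8 to 65.7) to 30.6 points (25.0 to 55.6) among the previously transfused. The other row would rest on 11 patients: even at 11/11 its lower limit is 0.025^(1/11) = 71.5%.

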6.3.2 Key secondary analysis

Kaplan-Meier estimates

An estimate of the survival function (i.e., time to relapse, duration of transfusion independence) will be constructed using Kaplan-Meier (product-limit) method as implemented in PROC LIFETEST with METHOD=KM option. The PROC LIFETEST statement will use the option CONFTYPE=LOGLOG.

Median survival will be obtained along with 95% confidence intervals calculated from PROC LIFETEST output using the method of [\[Brookmeyer and Crowley 1982\]](#). Kaplan-Meier estimates of the survival function with 95% confidence intervals at specific time points will be summarised. The standard error of the Kaplan-Meier estimate will be calculated using Greenwood's formula [\[Collett 1994\]](#).

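### Censoring a still-open longest transfusion-free interval treats a fully known value as incomplete, so the Kaplan-Meier median for this secondary endpoint is biased upward

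*SAP*

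**What the plan says.** SAP section 1.2 (Table 1-1) and Protocol section 3 (Table 3-1) define the endpoint within a window: the longest transfusion-free interval by 6 months and by 24 months. SAP 2.6.5 analyses the "duration of the longest interval without a platelet or RBC transfusion by 6 months and by 24 months (responders only"), for platelets and RBCs separately, and states that it "will be summarised using Kaplan-Meier analysis and the median longest duration will be presented along with 95% confidence interval".

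The interval may start at first dose or on the day after a transfusion, and it ends on the day before a transfusion. Otherwise, "if no end date of longest interval without a platelet or RBC transfusion occurs, the patient will be" censored at the last contact date. SAP 6.3.2 handles duration of transfusion independence with the same survival machinery as time to relapse, with a Brookmeyer-Crowley interval. Protocol 10.5.1 also says that the duration "will be summarised using Kaplan-Meier analysis" but gives no censoring rule.

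SAP 2.6.5 does not cut the by-6-month interval at 6 months. It also has no rule for a patient who dies with an open interval, and SAP 2.1.3 derives the last contact date only for patients not known to have died.

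**The concern.** Kaplan-Meier suits a duration whose end was not seen, provided the reason for not seeing it is unrelated to how long it would have lasted. Neither condition holds for a patient who completes the window. The longest interval by day 182 is a fact on day 182; later events cannot change it. The patient is nevertheless coded as censored exactly when the final open gap is the longest one, and that is typical of patients who have stopped needing transfusions.

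Kaplan-Meier then reads each of these values as a lower bound and moves the patient's weight to longer durations. The reported median therefore drifts above the quantity defined in the objectives table, and the drift grows with the share of patients who do well. SAP 2.6.5 repeats this summary by age and ethnicity, so subgroups with different censored shares could appear to differ for that reason alone.

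**Working it through.** **The plan's own figure.** SAP 2.6.5 states no number for this endpoint, so there is none to reproduce. The check applies the rule as written.

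**Two patients, each followed to day 182** (SAP formula: end date − start date + 1)

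- Patient A is transfused on days 10, 20, 30, 40, 50 and 60. The open gap runs from day 61 to day 182: 182 − 61 + 1 = 122 days. It is the longest, so A is **censored** at 122.
- Patient B is transfused on days 10, 20 and 120. The longest gap runs from day 21 to day 119: 119 − 21 + 1 = 99 days. The open gap is 182 − 121 + 1 = 62 days. B is an **event** at 99.

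Both values are completely known for a by-6-month endpoint. Only A, who did better, is treated as incomplete. If A were a non-responder last contacted 30 days later, on day 212, the uncut rule would record 212 − 61 + 1 = 152 days under a 6-month label.

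**Inputs for the size.** Follow-up is 182 days for everyone. The documents give no transfusion rate and no share of patients who stop needing transfusions, so these are assumed: exponential gaps with mean 7 to 20 days, and 20-60% of patients stopping on a day spread evenly over an early period (up to day 120, or days 14 to 150). Each scenario has 20,000 simulated patients. The direct median uses every patient's known longest interval. The Kaplan-Meier (KM) median uses the SAP event and censoring rule. Coverage is the share of 600 samples of 54 patients whose Brookmeyer-Crowley log-log 95% interval contains the direct median.

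Stopping on days 14 to 150:

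| Share stopping | Mean gap (days) | Direct median | KM median | Censored | Coverage |
|---|---|---|---|---|---|
| 20% | 10 | 35.9 | 36.5 | 25% | 0.94 |
| 40% | 10 | 43.4 | 46.2 | 43% | 0.95 |
| 50% | 10 | 51.0 | 70.0 | 51% | 0.92 |
| 60% | 10 | 66.8 | not reached | 61% | 0.72 |
| 20% | 20 | 57.1 | 60.0 | 28% | 0.92 |
| 30% | 20 | 60.7 | 65.4 | 36% | 0.91 |
| 40% | 20 | 66.2 | 75.5 | 44% | 0.89 |
| 50% | 20 | 73.3 | 105.5 | 53% | 0.79 |
| 60% | 20 | 82.8 | not reached | 61% | 0.59 |

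At 50% stopping the estimate is on the edge: the KM median was not reached in 44% (gap 10) and 40% (gap 20) of samples of 54.

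Across gaps of 7 to 20 days and both stopping patterns:

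- At 20-40% stopping, KM exceeds the direct median by about 0.3 to 10 days.
- At 46%, the excess is roughly 3 to 32 days. This figure is unstable: with a mean gap of 14 days and stopping up to day 120, repeat runs gave 83 against 67 days and 91 against 68.
- With stopping up to day 120, KM is not reached at 50%, where the direct median is about 66 to 84 days, or at 60%, where it rises to about 103.

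KM lay above the direct median in every scenario.

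**The case against.** The best defence is that some intervals really are incomplete. A patient who dies, withdraws or is lost before the window closes has an unfinished gap, and taking it at face value understates it. This stands. For responders who leave 30 days after relapse (assumed mean 365 days to relapse, with transfusions resuming about 60 days later), the plain observed median was 288.9 days against 320.9 had everyone been followed for 24 months. Censoring did not repair it, however: the KM median was 643.1. Any replacement needs an explicit rule for early leavers.

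The defence is also right that the error is small when few patients are censored, and that no test or decision rests on this endpoint.

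Three stronger readings are tempting, but the documents do not support them.

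- A reader might infer that Kaplan-Meier is to blame because the median grows with follow-up. With an unchanged process (mean gap 14 days), KM gives 41.6 days at 182 days and 60.8 at 730, a ratio of 60.8/41.6 = 1.46. The plain observed median gives 40.8 and 60.5, a ratio of 60.5/40.8 = 1.48. At most 7% of patients were censored. Growth with the window belongs to a longest-interval endpoint.
- A reader might infer that short-followed non-responders are pooled with responders at 24 months. Both documents restrict that summary to responders, and neither plans a comparison of 6 with 24 months.
- A reader might infer that the planned median is meaningless in all cases. With up to 40% of patients stopping, coverage in the table was 0.89 to 0.95.

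**Conclusion.** The point holds for patients who complete the window with their longest interval still open. Their values are known, the rule censors them because of the outcome itself, and the median is pushed upward. The missing cut at 6 months is a second, separate gap.

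The direction follows from the rule; the size rests on assumed transfusion patterns. The error is a few days, and up to about 10, when 20-40% stop needing transfusions. It becomes large, or leaves no median at all, when about half or more do. The assumed 20-60% overlaps the true response rates of 10-50% in SAP Table 3-2, but haematologic response is not the same as freedom from transfusion, so this is only a rough guide to where the trial may fall.

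The change is worth making before the final analysis. It does not touch the primary response rate, the transfusion-independence proportions or the proportions with any transfusion, none of which uses Kaplan-Meier.

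**What to change.** - Drop Kaplan-Meier for the longest interval. Cut intervals at 6 months (all patients) and 24 months (responders).
- Report the observed longest interval as a median with a distribution-free 95% confidence interval, quartiles and range, with days observed alongside.
- State how patients who die or leave before the window ends are handled, for example flagged and summarised with and without them.
- If a time-to-event result is wanted, keep Kaplan-Meier only for an interval with a defined start, such as from the day independence first qualifies (day 28 for platelets, day 56 for RBCs) to the next transfusion.
- Record the departure from Protocol 10.5.1 in SAP section 4. SAP section 1 shows that the 6-month lock has passed and the primary study report is written, so label any revised 6-month result as changed after that report.

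The cost is revised SAP wording, a documented departure from the protocol, and reprogramming of this table and its age and ethnicity versions. No new data are needed. The result becomes purely descriptive, and the 6-month figure may differ from the one already reported.
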